16.2. SECONDARY EFFICACY

The secondary efficacy analyses will be performed for the ITT and PP population.

16.2.1. SECONDARY EFFICACY VARIABLE & DERIVATIONS

Document:

Author:

Version Number:
Version Date:

V2.0

21MAY2020

Template No: CS_TP_BS016 Revision 4
Effective Date: 01Apr2016

Reference: CS_WI_BS005

16.2.1.1. Change from baseline in Clinical Global Impression Bipolar Version, Severity of Illness (CGI-BP-S) Score (Depression) at Week 6

The CGI-BP-S is a clinician-rated assessment of the subject's current illness state on a 7-point scale, where a higher score is associated with greater illness severity. The CGI-BP-S score takes one of the following values: 1 (normal, not at all ill), 2 (borderline mentally ill), 3 (mildly ill), 4 (moderately ill), 5 (markedly ill), 6 (severely ill), 7 (among the most extremely ill patients). CGI-BP-S is assessed at Visit 2/Baseline/Week 0, Visit 3/Week 1, Visit 4/Week 2, Visit 5/Week 4, and Visit 6/Week 6.

16.2.2. MISSING DATA METHODS FOR SECONDARY EFFICACY VARIABLE(S)

The secondary efficacy variable, change from baseline in CGI-BP-S depression score at Week 6, will be set to missing if the CGI-BP-S depression score at Week 6 is missing or baseline value is missing. The same applies to all other visits. The analysis of the secondary efficacy variable will use a MMRM which makes an MAR assumption to the missing secondary efficacy endpoints. Early termination data will be mapped as described in [Section 6.3](#). Missing data will not be imputed.

16.2.3. ANALYSIS OF SECONDARY EFFICACY VARIABLE

The secondary efficacy estimand for this study is the difference in means of change from baseline in the CGI-BP-S depression score at Week 6 comparing each SEP-4199 treatment group to placebo in ITT population with major depressive episode associated with bipolar I disease (bipolar I disorder) at sites located in US and Europe defined through the inclusion/exclusion criteria, should a subject be able to tolerate and adhere to treatment up to Week 6.

The efficacy of SEP-4199 in terms of the CGI-BP-S depression score will be evaluated using the following two null hypotheses:

H3: There is no difference in mean change from baseline at Week 6 on the CGI-BP-S depression score in the SEP-4199 200 mg treatment arm compared to Placebo.

H4: There is no difference in mean change from baseline at Week 6 on the CGI-BP-S depression score in the SEP-4199 400 mg treatment arm compared to Placebo.

The alternative hypothesis for each of the null hypotheses is that there is a difference.

The CGI-BP-S depression score will be analyzed by the MMRM method described for the primary efficacy endpoint with baseline CGI-BP-S depression score used as covariate (see [Section 16.1.3](#)) for the ITT population. LS mean of change from baseline over time will be plotted including p-value.

The CGI-BP-S mania and overall bipolar illness scores will only be presented in listings.

16.2.4. SENSITIVITY ANALYSIS OF SECONDARY EFFICACY VARIABLE

Sensitivity analysis similar to the one described in [Section 16.1.4](#) will also be produced for the secondary endpoint for the ITT population. See [APPENDIX 3](#) for details.

Document:

Author:

Version Number:

V2.0

Version Date:

21MAY2020

Template No: CS_TP_BS016 Revision 4
Effective Date: 01Apr2016

Reference: CS_WI_BS005

16.2.5. SUPPORTIVE ANALYSIS OF SECONDARY EFFICACY VARIABLE

ANCOVA and analysis on PP population as described in [Section 16.1.5](#) will also be produced for the secondary endpoint.

16.2.6. SUBGROUP ANALYSIS OF SECONDARY EFFICACY VARIABLE

The same subgroup analysis as the one performed for primary analysis will be performed with the secondary endpoint (see [Section 16.1.6](#)) for the ITT population.

16.3. OTHER EFFICACY VARIABLES

All other efficacy endpoints will be analyzed using the ITT population.

16.3.1. OTHER EFFICACY VARIABLE DERIVATIONS

16.3.1.1. Hamilton Rating Scale for Anxiety (HAM-A)

The HAM-A is a rating scale developed to quantify the severity of anxiety symptomatology. The 14 items are: anxious mood, tension, fears, insomnia, intellectual, depressed mood, somatic (muscular), somatic (sensory), cardiovascular symptoms, respiratory symptoms, gastrointestinal symptoms, genitourinary symptoms, autonomic symptoms, and behavior at interview. Each of the 14 items is rated on a 5-point scale, ranging from 0 (not present) to 4 (very severe). The HAM-A total score is the sum of the 14 individual items and ranges from 0 to 56. A higher score is associated with a greater degree of anxiety. A score of ≥ 14 has been suggested to indicate clinically significant anxiety ([Rush 2000](#)). If 1 or more items are missing at a visit, the total score will be set to missing. HAM-A is assessed at Visit 2/Baseline/Week 0, Visit 3/Week 1, Visit 4/Week 2, Visit 5/Week 4, and Visit 6/Week 6.

16.3.1.2. Quick Inventory of Depressive Symptomatology – Self-Report 16-Item (QIDS-SR16)

The QIDS-SR16 is a 16-item self-report measure of depressive symptomatology which uses a computerized assessment interface for administration. The scoring system for the QIDS-SR16 converts responses from 16 separate items into nine DSM-IV symptom criterion domains. Each item is rated 0 to 3. For symptom domains that consist of more than one item, the highest score among the items relevant to the given domain is taken. The total score equals the sum of the nine individual domain scores and ranges from 0 to 27. Higher score indicates worse depression symptoms. The nine domains comprise: depressed mood (Item 5); concentration/decision making (Item 10); self outlook (Item 11); suicidal ideation (Item 12); decreased interest (Item 13); decreased energy (Item 14); sleep disturbance (initial, middle, and late insomnia or hypersomnia) (Items 1 to 4); appetite/weight disturbance (Items 6 to 9); and psychomotor disturbance (Items 15 and 16). The total score will be set to missing if one or more domain scores are missing at a visit. The appetite/weight disturbance symptom domain score will be set to missing if three or more items are missing at a visit, given the planned skip pattern of items 6 to 9, and the remaining symptom domain scores will be set to missing if one or more items within the

Document:

Author:

Version Number:

V2.0

Version Date:

21MAY2020

Template No: CS_TP_BS016 Revision 4
Effective Date: 01Apr2016

Reference: CS_WI_BS005

respective domain are missing. QIDS-SR16 is assessed at Visit 2/Baseline/Week 0, Visit 3/Week 1, Visit 4/Week 2, Visit 5/Week 4, and Visit 6/Week 6.

16.3.1.3. Sheehan Disability Scale (SDS)

Three items are self-rated using an 11-point visual analog scale ranging from 0 to 10 to assess disability across three domains: work/school, social life, and family life; the three items will be summarized individually in addition to the SDS total score. The SDS total score is calculated as the sum of the 3 items and ranges from 0 (unimpaired) to 30 (highly impaired). If one or more items are missing at a visit, as can occur when a subject opts out of the work/school item because it does not apply, the authors of the scale recommend setting the total score to missing ([Sheehan 2008](#)). Number of days lost due to symptoms, and number of days underproductive due to symptoms are also collected. SDS is assessed at Visit 2/Baseline/Week 0 and Visit 6/Week 6.

16.3.1.4. EuroQoL 5-D (EQ-5D-5L)

The EQ-5D-5L is a standardized instrument developed by the EuroQol Group as a measure of health-related quality of life that can be used in a wide range of health conditions and treatments. The EQ-5D consists of a descriptive system and the EQ VAS.

The descriptive system comprises five dimensions: mobility, self-care, usual activities, pain/discomfort and anxiety/depression. Each dimension has 5 levels: no problems, slight problems, moderate problems, severe problems and extreme problems, corresponding to scores of 1 to 5, respectively. The patient is asked to indicate his/her health state by ticking the box next to the most appropriate statement in each of the five dimensions. This decision results in a 1-digit number that expresses the level selected for that dimension. The digits for the five dimensions can be combined into a 5-digit number that describes the patient's health state. An index value (a weighted scoring of the 5 dimension scores with a possible range from 0 to 1) will be assigned to each observed health state using the US value set as defined in [APPENDIX 8](#).

The EQ VAS records the patient's self-rated health on a vertical visual analogue scale, where the endpoints are labeled 'The best health you can imagine' and 'The worst health you can imagine'. The VAS can be used as a quantitative measure of health outcome that reflect the patient's own judgment. EQ-5D-L is assessed at Visit 2/Baseline/Week 0 and Visit 6/Week 6.

16.3.1.5. MADRS responders

A MADRS responder is defined as achieving a $\geq 50\%$ reduction from the baseline total score at Week 6. The MADRS total score percentage change will be defined as $(\text{value at postbaseline visit} - \text{baseline value}) \times 100 / (\text{baseline value})$. Subjects having a negative percentage change indicate improvement in MADRS total score.

Any ITT subject with missing response at Week 6 will be classified as non-responder. As a sensitivity analysis, the same analysis will be repeated by excluding subjects with missing responses, where applicable.

In addition, the following endpoints will be explored through graphing:

- Subjects achieving a $\geq 40\%$ reduction from the baseline total score at Week 6;

Document:

Author:

Version Number:

V2.0

Version Date:

21MAY2020

Template No: CS_TP_BS016 Revision 4
Effective Date: 01Apr2016

Reference: CS_WI_BS005

- Subjects achieving a $\geq 30\%$ reduction from the baseline total score at Week 6;
- Subjects achieving a $\geq 20\%$ reduction from the baseline total score at Week 6.

16.3.1.6. MADRS remission

A MADRS remission is defined as a MADRS total score of ≤ 12 at Week 6.

Any ITT subject with missing MADRS total score at Week 6 will be classified as non-remitter. As a sensitivity analysis, the same analysis will be repeated by excluding subjects with missing MADRS total score at Week 6, where applicable.

Additionally, subjects with MADRS total scores ≤ 10 and ≤ 8 at Week 6 are of interest.

16.3.1.7. Young Mania Rating Scale (YMRS)

The YMRS is an 11-item instrument used to assess the severity of mania in patients with a diagnosis of bipolar disorder. The 11 items are: Elevated Mood, Increased Motor Activity Energy, Sexual Interest, Sleep, Irritability, Speech (Rate and Amount), Language-Thought Disorder, Content, Disruptive-Aggressive Behaviour, Appearance and Insight. The YMRS is a clinician-rated assessment. Ratings are based on patient self-reporting, combined with clinician observation (accorded greater score). Seven items are rated on a 5-point scale, ranging from 0 to 4, and four items are rated on a 9-point scale, ranging from 0 to 8. The YMRS total score is the sum of the 11 individual items and ranges from 0 to 60. A higher score is associated with a greater severity of mania. If one or more items are missing at a visit, the total score will be set to missing. YMRS is assessed at Visit 1/Screening, Visit 2/Baseline/Week 0, Visit 3/Week 1, Visit 4/Week 2, Visit 5/Week 4, Visit 6/Week 6, and Visit 7/Follow-up/Week 7.

16.3.2. MISSING DATA METHODS FOR OTHER EFFICACY VARIABLE(S)

Any individual missing item in any scale will not be imputed.

For HAM-A, SDS, and YMRS, if 1 or more items are missing at a visit, the total score will be set to missing. Similarly, if an individual domain score for EQ-5D-5L is missing, the index value cannot be calculated.

For QIDS-SR16, the total score will be set to missing if 1 or more domain scores are missing at a visit. The appetite/weight disturbance symptom domain score will be set to missing if 3 or more items are missing at a visit, given the planned skip pattern of items 6 to 9, and the remaining symptom domain scores will be set to missing if 1 or more items within the respective domain are missing.

For MADRS responder, any ITT subject with a missing response at Week 6 will be classified as a non-responder.

For MADRS remission, any ITT subject with a missing MADRS total score at Week 6 will be classified as a non-remitter.

16.3.3. ANALYSIS OF OTHER EFFICACY VARIABLES

Document:

Author:

Version Number:

V2.0

Version Date:

21MAY2020

Template No: CS_TP_BS016 Revision 4
Effective Date: 01Apr2016

Reference: CS_WI_BS005

16.3.3.1. Change from baseline in HAM-A total score at Week 6

The HAM-A total score and change from baseline will be summarized by time point for each treatment group. Change from baseline at Week 6 will be analyzed by the MMRM method described for primary endpoint with baseline HAM-A total score as covariate (see [Section 16.1.3](#)).

Change from baseline at Week 6 will be analyzed by the ANCOVA model described in [Section 16.1.5.1](#) with baseline HAM-A total score as covariate.

16.3.3.2. Change from baseline in QIDS-SR16 total score at Week 6

The QIDS-SR16 total score and change from baseline will be summarized by timepoint for each treatment group. Change from baseline at Week 6 will be analyzed by the MMRM method described for primary endpoint with baseline QIDS-SR16 total score as covariate (see [Section 16.1.3](#)).

Change from baseline at Week 6 will be analyzed by the ANCOVA model described in [Section 16.1.5.1](#) with baseline QIDS-SR16 total score as covariate.

16.3.3.3. Change from baseline in SDS total score at Week 6

The SDS total score and change from baseline will be summarized by time point for each treatment group. Change from baseline at Week 6 will be analyzed by the ANCOVA model described in [Section 16.1.5.1](#) with baseline SDS total score as covariate.

In addition, the following composite variables will be summarized: days = 0 at baseline, days at Week 6 ≥ 1 ; days ≥ 1 at baseline, days at Week 6 = 0; days = 0 at baseline, days at Week 6 ≥ 3 ; days ≥ 3 at baseline, days at Week 6 = 0. Results for these composite variables will be evaluated using logistic regression utilizing a 0-1 indicator (1 = met the criteria, 0 = did not meet the criteria) as the dependent variable, treatment and region as categorical factors, and baseline SDS total score as a covariate. If the model fails to converge, the model will be attempted without region first, and if still not converging then without baseline SDS total score. Contrasts will be evaluated for each treatment group compared to placebo. Odds Ratios, 95% CIs and Wald chi-square p-values will be presented for each contrast. Only n and percent will be presented in cases where the number of subjects meeting the above composite variable criteria is too small for an analysis to be performed. A Cochran-Armitage trend test will also be conducted on this outcome across placebo and the treatment groups.

16.3.3.4. Change from baseline in EQ-5D-5L Scores at Week 6

The EQ dimension scores, VAS score, and index score and change from baseline will be summarized by time point for each treatment group. Change from baseline of EQ VAS and index score at Week 6 will be analyzed by the ANCOVA model described in [Section 16.1.5.1](#) with baseline EQ VAS and baseline index score as a covariate, respectively.

16.3.3.5. MADRS responders at Week 6

For MADRS responder, any ITT subject with missing response at Week 6 will be classified as Non-responder. As a sensitivity analysis, the same analysis will be repeated by only using observed values and not including subjects with missing responses. This sensitivity analysis will be repeated by removing remote visits due to COVID-19.

Document:

Author:

Version Number:

V2.0

Version Date:

21MAY2020

Template No: CS_TP_BS016 Revision 4
Effective Date: 01Apr2016

Reference: CS_WI_BS005

The MADRS total score responder proportions at Week 6 will be compared among the 3 treatment groups using logistic regression. This model will include treatment and region as fixed effects and baseline MADRS score as a covariate. If the model fails to converge, the model will be attempted without region first, and if still not converging then without baseline MADRS total score. Effect size and Number Needed to Treat (NNT) will be provided.

Between group effect size will be defined as: Natural Log(odds ratio)xsqrt(3)/pi

The NNT will be derived as 1/Risk Reduction where Risk Reduction (RR) = (SEP-4199 trt group – placebo response rate). The NNT results will be provided in whole numbers with any fractional values rounded up to the nearest whole number.

The 95% CI will also be presented (only when the lower and upper limits are of the same sign) and are computed by taking the reciprocal of the 95% lower and upper bound of the RR. The lower confidence limit will be rounded down to the largest integer value that is less than the computed estimate, and the upper confidence limit will be rounded up to the smallest integer value that is greater than the computed estimate.

Cochran-Armitage test for trend will be used to test for association between MADRS response and the three treatments.

The log rank testing method will be used to test for differences among the treatments for time to MADRS response. ITT subjects discontinuing the study and those completing the study without meeting the criteria for MADRS response will be censored at the date of last dose of study drug or, if unknown, the end of study date. The analysis will be supplemented with Kaplan-Meier curves to illustrate the differences among the three treatments. A Cox proportional hazards model will also be used with treatment, region, and baseline value as parameters. Wald Chi-square p-value will be included.

A cumulative distribution curve for all treatment groups will be presented, plotting the cumulative percent of MADRS responders versus the percent reduction at Week 6 from baseline.

16.3.3.6. MADRS remission at Week 6

Remission incidence rate, defined as MADRS total score ≤ 12 , will be analyzed similarly to the MADRS responder analysis, including the sensitivity analysis of observed values and of assessing the removal of remote visits (see [Section 16.3.3.5](#)).

Subjects with MADRS total scores ≤ 10 and ≤ 8 at Week 6 will be summarized using descriptive statistics.

A cumulative distribution curve for all treatment groups will be presented, plotting the cumulative percent of MADRS remissions versus the MADRS total score at Week 6.

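### The two SDS recovery composites count subjects with no lost days to recover as non-recoverers, which pulls the odds ratio toward 1 and costs power in an exploratory analysis

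*SAP*

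**What the plan says.** SAP 16.3.3.3 adds four binary outcomes to the SDS total score analysis. The list opens with "the following composite variables will be summarized: days = 0 at baseline". Two describe new loss (0 days at baseline, then at least 1 or at least 3 at Week 6). Two describe recovery, for example "days ≥ 1 at baseline, days at Week 6 = 0"; the other starts from at least 3 days.

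Each outcome is modelled by logistic regression "utilizing a 0-1 indicator (1 = met the criteria, 0 = did not meet the criteria) as the dependent variable", with "treatment and region as categorical factors, and baseline SDS total score as a covariate". Odds ratios, 95% confidence intervals and Wald p-values are promised, plus a Cochran-Armitage trend test. A fallback covers sparse data: "Only n and percent will be presented in cases where the number of subjects meeting the above composite variable criteria is too small".

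The population comes from SAP 16.3: "All other efficacy endpoints will be analyzed using the ITT population". Neither section limits the denominator to subjects who meet the baseline condition.

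Two further facts come from SAP 16.3.1.3. First, two day counts exist: "Number of days lost due to symptoms, and number of days underproductive due to symptoms are also collected". Section 16.3.3.3 does not say which one is meant. Second, the SDS total is set to missing when an item is missing, "as can occur when a subject opts out of the work/school item because it does not apply".

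**The concern.** A subject with 0 days at baseline cannot satisfy a recovery criterion, whatever the treatment does. Under the written coding that subject gets a 0, the same value as someone who had lost days and did not recover. The modelled event rate is then the recovery rate multiplied by the share of subjects who had anything to recover from.

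A reader of the output will take the odds ratio as the odds of recovery among impaired subjects. It is not that quantity: it lies closer to 1, and the test behind it has less power than the same data could give. The trend test uses the same outcome and has no covariate, so nothing offsets the dilution there.

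**Working it through.** The documents state no rate, odds ratio or power for these composites, so there is no plan figure to reproduce on this point. The sample-size input does check: simulating the primary power at 93 per arm, effect size 0.44 and truncated Hochberg with gamma 0.9 gives 90.5% (at least one comparison) and 75.1% (both), against the stated values of about 90% and 75%.

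**Inputs.** From the SAP: 1:1:1 allocation, 93 evaluable per arm (rounded to 90 in the first table), two-sided 5%. Assumed, because the documents give neither: the share q meeting the baseline condition, taken as equal between arms, and the event rates a and b among those subjects.

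**Formulas.** As coded, the arm rates are qa and qb, with n per arm. In the at-risk set they are a and b, with nq per arm.

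- Risk ratio: qa/qb = a/b, so it is unchanged.
- Coded odds ratio: (a/b) × (1 − qb)/(1 − qa). For q < 1 this is closer to 1 than (a/b) × (1 − b)/(1 − a).
- Power: Φ(|difference|/SE − 1.96), with SE = √{[p1(1 − p1) + p0(1 − p0)]/n}.

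**Recovery, a = 0.60, b = 0.40, 90 per arm.** The at-risk odds ratio is 1.5 × 0.60/0.40 = 2.25.

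| q | Coded rates | Coded OR | Power as coded | At-risk n per arm | Power in at-risk set |
|---|---|---|---|---|---|
| 0.4 | 0.24 vs 0.16 | 1.5 × 0.84/0.76 = 1.66 | 27% | 36 | 41% |
| 0.6 | 0.36 vs 0.24 | 1.5 × 0.76/0.64 = 1.78 | 43% | 54 | 56% |
| 0.8 | 0.48 vs 0.32 | 1.5 × 0.68/0.52 = 1.96 | 60% | 72 | 69% |

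First row in full. As coded, SE = √[(0.1824 + 0.1344)/90] = 0.0593, and 0.08/0.0593 − 1.96 = −0.61, giving 27%. At risk, SE = √(0.48/36) = 0.1155, and 0.20/0.1155 − 1.96 = −0.23, giving 41%. The restricted analysis has more power although it has fewer subjects.

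**Other rates, 93 per arm, q from 0.2 to 0.9** (same comparison, with the pooled-variance SE under the null):

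| Composite | Assumed rates | At-risk OR | Coded OR | Power lost (points) |
|---|---|---|---|---|
| Recovery | 70% vs 50% | 2.33 | 1.47 to 2.08 | 6 to 19 |
| Recovery | 50% vs 30% | 2.33 | 1.74 to 2.21 | 3 to 11 |
| New loss | 10% vs 25% | 0.33 | 0.34 to 0.39 | 1 to 4 |
| New loss | 5% vs 15% | 0.30 | at most 0.33 | 0.5 to 1.5 |

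The driver is how common the event is among those at risk. If new loss were as frequent as 20% versus 40%, the cost would rise to about 8 points at q = 0.5.

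**Does the planned covariate repair it?** Only in part. Logistic regressions were simulated with treatment, region and a baseline SDS score correlated with at-risk status. At q = 0.5, 70% versus 50% and correlation 0.8, the median adjusted odds ratio was 1.82 in all ITT subjects against 2.38 in the at-risk set, with power 37% against 49%.

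**The case against.** **The denominator is not stated outright.** Section 16.3.3.3 names none, and SAP 8 leaves table layout to templates that are not in the documents, so the programmers may intend the at-risk set. That is possible, but the written rule is a two-level indicator in the ITT population, and following it gives the diluted result. Where the SAP wanted a third level it wrote one: the mania indicator in SAP 17.6.1 is 1, 0 or missing.

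**The stakes are low.** This stands. The composites are not among the listed endpoints in either document, lie outside the multiplicity procedure (SAP 7.4) and carry no power target.

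Three stronger readings are tempting, and the documents do not support them.

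- *Bias or false positives.* With 50% recovery in both arms but 65% versus 55% at risk, the coded rates are 0.325 and 0.275 and the unadjusted odds ratio is (0.325/0.675)/(0.275/0.725) = 1.27. A reader might call that a spurious treatment effect. It is sampling error: the all-ITT comparison is still randomized, the null is preserved across randomizations, and type I error is not inflated.
- *All four composites mishandled alike.* In the new-loss pair a 0 is the favourable result, so ineligible subjects are not counted as failures, and the loss is small unless new loss is common.
- *Usable data from non-workers discarded.* Subjects with no baseline SDS total do leave a complete-case model. SAP 16.3.1.3 does not say that people who skip the work/school item supply day counts, so that is an assumption.

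**Conclusion.** The point holds for the two recovery composites, as a loss of precision and interpretability in exploratory analyses. Over the rates tried, power falls by 3 to 19 points and an at-risk odds ratio of about 2.3 shrinks to between 1.5 and 2.2. For the two new-loss composites the direction is the same, but the cost is about 0.5 to 4 points when new loss is uncommon. No primary or secondary conclusion is touched.

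The direction needs only that some subjects fall outside the baseline condition, in equal shares across arms. The size rests on assumed at-risk shares and event rates and, in the first table, on an unadjusted comparison. A desirable correction, not an essential one.

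**What to change.** In SAP 16.3.3.3:

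1. Restrict each composite, its logistic model and its Cochran-Armitage test to subjects meeting that composite's baseline condition: 0 days for both new-loss outcomes, at least 1 or at least 3 days for the respective recovery outcome. These sets are fixed before treatment, so the randomized comparison is kept.
2. State whether days means days lost or days underproductive, or that both are analysed. The sets cannot be built until this is settled.
3. For the two recovery composites only, replace the baseline SDS total with the baseline day count, and name it in the non-convergence fallback. For the new-loss composites add no day-count covariate: it is constant at 0 in that set and cannot be estimated.

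The cost is a filter per composite, one changed covariate in two models, and a smaller displayed N. Restriction removes only subjects who could not have scored 1, so the count meeting each criterion, on which the sparse-data rule depends, does not change.
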